#### Test Subject Recruitment

ICR has been conducting repellent studies for over twenty years. During this time ICR has amassed a large list of potential study subjects. These subjects also refer friends and colleagues to us. When a repellent study date has been established, ICR will contact potential study subjects by telephone and

Page 17 of 31

<sup>2 L.C. Rutledge and R. K. Gupta, 1999, Variation in The Protection Periods of Repellents on Individual Human Subjects: An Analytical Review, Journal of the American Mosquito Control Association, 15(3):348-355

Protocol No.: G0590307001A044 ICR Project No.: 0307-059-0155

briefly discuss the study, the date of the study, and location. Any study specific inclusion/exclusion requirements will also be mentioned at this time. When the number of interested subjects required for a particular study has been met, ICR will stop recruitment.

ICR uses the following initial telephone script to recruit test subjects:

"ICR will be conducting a repellent project on these dates, (Month, Day(s), Year), at (exact study site) would you be available to participate in this study?"

If the potential test subject is available, the inclusion/exclusion criteria will be discussed in detail and verified whether the subject qualifies to participate. The ICD will also be discussed with the test subject at this time. In addition, ICR will mail a copy of the ICD to each interested test subject for their review. They will be instructed to contact the P.I. to verify receipt of the ICD and to ask any ICD or study related questions they may have.

The P.I. will contact all interested subjects by phone several days after receipt of the ICD to fully explain the ICD with them. All contacted people that show interest will be offered the opportunity to come to ICR to go through the consent process in person. If interested subjects are unable to travel to ICR, the consent process will be conducted on the phone. Sufficient time will be spent with each interested subject to answer any questions they may have. When both the P.I. and the interested subject are satisfied that they have meet the study qualifications for inclusion into the study, understand and are comfortable with the ICD, they will then be invited to sign the ICD. Each subject will be asked to sign and date the ICD in the presence of a witness. Their signature will acknowledge that they have been informed and freely give their consent to participate in the study. The witness will then sign and date the ICD. Each test subject giving their consent by phone will be asked to mail the signed ICD back to ICR. A copy of the signed ICD will be provided to each study subject, either by mail or in person depending upon whether consent was in person or by phone.

When a subject is available, and qualifies for a particular study, and is willing to participate based on study requirements as explained, and has signed an ICD, they will be notified of study specific travel arrangements in a follow up call closer to the study date.

ICR has been fully compliant with 40 CFR 26.1125 in obtaining written approval for all repellent studies from an independent Institutional Review Board

In the event that an interested subject declines to sign an informed consent document, they will not be permitted to participate in the study.

There is no coercion for any subject to participate. The inclusion/exclusion criteria are clear, the payment is clear, the subjects are informed of the conditions they will likely encounter and what is

Page 18 of 31

Protocol No.: G0590307001A044 ICR Project No.: 0307-059-0155

expected of them. Each consenting test subject will be informed that they may drop out of the study at any time. Further, they may leave as soon as practical after early withdrawal from the test.

#### **METHODS**

#### Experimental Design

This is a subject-blinded study. The delineated areas on the arms of subjects will be treated and used as test areas. Only arms are being treated in this study, in an attempt to further reduce the areas available for mosquitoes to bite. In addition, arms are quite easy to monitor for mosquito activity. Therefore there will be twelve test arms for each treatment. Each test subject will have one arm treated with one of the two test products and the other arm will be treated with the other test product.

#### Test site location:

The test locations at each test site will be selected before the study is to start. The principal criterion will be landing rates in the range of 1 to 10 per minute in a 250cm² area on an exposed untreated arm over a five minute period. Landing rates will be determined by the support staff, and/or the Study Director, who will expose an untreated arm (one per person) at likely sites throughout the test area.

Test site selection criteria will be based on unobstructed space and acceptable mosquito species composition. The repellents will be evaluated at one or more sites depending on landing rates observed and verified by ICR staff. At least two test sites will be selected for each day's testing. The sites will be rotated if necessary in order to maintain adequate biting pressure.

If previous observation has determined that the length of the mosquito activity period is less than the twelve hours required for the test, the test subjects will be treated early enough before mosquito activity begins to allow the end of their twelve-hour exposure period to correspond to peak, or nearly peak, mosquito activity. If the products successfully repel all mosquitoes at the end of the twelve-hour exposure period, the conclusion will be made that they would have provided complete repellency for the entire exposure period. The control subjects will monitor mosquito activity for the entire twelve hours. Test subjects and controls will be directed to positions along or adjacent to a trail or similar accessible habitat.

## Blinding of the Study

The test samples will be coded as "A" and "B". During the test these codes will be the only test sample designation referred to or that the test subjects will see. The Study Director and members of the ICR staff will know the actual test samples, but will refrain from such identifications in the field.

#### Treatment Groups

There will be two groups for each test location(Georgia and Florida): a treated group of twelve subjects whose arms will be treated, and an untreated (control) group of two test subjects whose arms will be untreated. Subjects will be given a subject number. They will be assigned to the groups by lottery selection of the subject number.

Page 19 of 31

Protocol No.: G0590307001A044 ICR Project No.: 0307-059-0155

Personnel preparation

All test subjects will complete and will sign an "Informed Consent Document" prior to acceptance as a test participant.

On the evening prior to the first day of testing, the outside of the shoes of each test subject, the controls and the ICR staff will be treated with a 0.5% permethrin aerosol to help prevent ticks from crawling on test participants in the test areas. This treatment will not affect the test but will help protect the people involved from ticks. Permethrin has a low vapor pressure and will not interfere with the repellency of the treated arms.

Females will be required to perform an over the counter pregnancy test that will be supplied by ICR. They will do this the morning of the test. The results will be verified by a qualified female ICR staff member. They may not participate if they are pregnant or breastfeeding. The results of this pregnancy test will be kept confidential and will not be disclosed to anyone other than the test subject and the P.I..

The evening before the study is scheduled to begin, the test subject's arms will be measured in the following manner for demarcation of the 250 cm^2 test area:

#### For Arms:

The subject's elbow will be placed on a flat rigid surface with the forearm held perpendicular to that surface. A mark will be made on the upper forearm 3" from the flat surface. A second mark will be made on the lower forearm at a point just below the wrist bone. The circumference of the arm will be measured at each of these points. The average of the two circumferences will be calculated. This represents the approximate circumference at the center point between the two marks. A third mark will be made at the center point between the two marks. The average circumference will be divided into 250cm², the total exposed surface area required for the test. This will yield the length of arm required to be exposed. The end points of this length of exposure area will be marked on the forearm so that each end point is equidistant from the center point. The endpoint measurements from the center point will be recorded so that they may be duplicated in the field. The distance from the tip of the little finger to the center point will be measured and also recorded so that the center point may be duplicated in the field.

The above mentioned measurements will be recorded on a repellent measurement form. If a test subject has been previously measured, the existing measurements will be used.

Prior to arrival at the field test site, the twelve test subjects and the two controls will wash their arms with unscented Neutrogena® soap. The test subjects and the control subjects will have 250 cm² areas delineated around their forearms and these arms will be prepared for treatment. The skin above and below the target area will be protected with elastic bandages and or Velcro® straps held in place with Elastikon® tape. Arms will be protected by shirt sleeves. Latex or vinyl gloves will be given to the

Page 20 of 31

Protocol No.: G0590307001A044 ICR Project No.: 0307-059-0155

subjects to protect their hands. Head nets will also be supplied to protect their heads and necks. The control test subjects will follow the same procedure but only on one arm. Determination of which arm the control subjects will use will be randomly selected by flipping a coin.

## Determination of Landing Rate

Biting pressure during the test day will be determined from the landing rate on the controls' arm during one minute periods for up to five-minutes. Once the landing rate has been confirmed (1 to 10 per minute) the counts will cease when that minute period expires. The landing rate verification will be conducted at, approximately, one-half hour intervals throughout each test day.

A whole body count of mosquito landings on one of the control subjects will be taken at the initiation of the test and then hourly. The whole body count will be conducted by having the designated control subject stand with their arms fully extended away from their sides. An ICR staff will record the number of mosquitoes that land in each of four areas on the test subject. These areas will be defined

Page 21 of 31

Protocol No.: G0590307001A044 ICR Project No.: 0307-059-0155

by an imaginary line through the midpoint in the front and back of the test subject from their head to the ground. An ICR staff will record the number of mosquitoes that land in one minute (15 seconds for each area). Counts will be taken and recorded to aid in quantifying the mosquito numbers in the test area.

### Criteria for Test End Point

Efficacy will be evaluated by intermittent exposure of the test subjects' arms. The treated test subjects will expose their treated arms to mosquitoes for 5 minutes at approximately 30 minute intervals. At the end of each 5 minute exposure period, the treated and control subjects will be escorted back to screened enclosures where they will be seated until the next 5 minute exposure period. The test subjects will expose treated arms until the FCB (when two bites occur on the same arm in the same exposure period, or one bite occurs in each of two consecutive exposure periods, the first bite being the confirmed bite) or until 12 hours have elapsed, whichever occurs first. For the purposes of this test, a bite is defined as a mosquito penetrating the skin with its proboscis and taking sufficient blood to cause its abdomen to swell. When the two bites have occurred as noted above, the test will terminate on that arm.

When the testing is terminated for an arm, test subjects will then roll down their sleeves to cover such discontinued arms. The test will be terminated on a treated arm when a bite is followed by one additional bite (the initial bite and one confirming bite). Each bite must occur within one 5 minute exposure period or one bite must occur in each of two consecutive exposure periods. If the bites do not occur within the specified time, the number of bites required will begin anew.

Once a confirmed bite occurs, the test subjects will stop exposing that arm to mosquitoes. They will then be able to remove the bandages and tape, scratch and wash that arm. If they want to, they can use rubbing alcohol to help stop the itching from the bites they may have received. Caladryl® or Calamine® lotion may also be used.

## Criteria for Test Cancellation

The study could be cancelled for several reasons; the first would be inclement weather. If weather conditions on site present unsafe circumstances for test personnel the study will be cancelled. These conditions include severe storm threats, high wind, or threat of lightning.

Additional reasons for test cancellation would be insufficient target insect activity. Any health concerns, the presence of WNV, or test material related reactions could also be reason for cancellation.

### On-Site Data Collection

The Study Director, or his designee, will record or ensure that temperature, relative humidity, wind speed and cloud-cover are recorded at least hourly throughout the test. Temperature and relative humidity will be obtained by using a sling psychrometer. The wind speed will be obtained by using

Page 22 of 31

Protocol No.: G0590307001A044 ICR Project No.: 0307-059-0155

an anemometer and cloud cover will be by a visual estimate. This data will be recorded on the Environmental Data Sheet by an ICR staff member.

The test subjects will be positioned in pairs. Each pair will be seated on a stool approximately 1 to 3 meters apart or the pair may move about by slowly walking in the area, but remaining within approximately 1 to 3 meters of each other. Each test subject will assist their partner in alerting him/her to mosquito landings on hard to see parts of their arms. When a test subject believes a bite is occurring, he/she will notify the Study Director or an ICR staff member for verification. ICR staff have been trained through in-house seminars. Their supervisor will have verified their training to recognize and discern between probes and bites. To ensure data integrity only ICR staff will record the time each bite occurs and any additional data required for this study.

The Study Director, QA representative and the ICR staff assistants will observe test subjects from a distance of approximately 1 to 3 meters. The controls will leave the immediate area as soon as the periodic landing rate has been determined or may remain in the vicinity. When a volunteer believes that a landing has occurred, the Study Director or the ICR assistant will approach close enough to determine when a bite has occurred.

Each test subject will be provided with a stool, a head net, latex or vinyl gloves, and a clip-board and ICR Repellency Test Data Sheets for recording the bites. Only ICR staff will verify and record the time of any bite that occurs.

Mosquitoes landing upon control subjects or ICR staff will be periodically aspirated into 9-dram vials and held for subsequent identification. Specimens will be collected from landings on the ICR staff at both sites and returned to the laboratory for identification by a Board Certified Entomologist.

At the conclusion of the study, ICR staff will inspect the clothing of all test participants for ticks.

Protocol No.: G0590307001A044 ICR Project No.: 0307-059-0155

## CONFIDENTIALITY

The information obtained from test subjects taking part in this test may be used by ICR and its sponsor and may become part of a report. This report will be kept as confidential as possible under local, state and federal law. The test subjects' first name and the first initial of their last name only may be referenced. ICR cannot guarantee that their identity will be kept confidential. Essex Institutional Review Board has the right to review their records.

#### DATA ANALYSIS:

Efficacy data will be reported as Protection Time which is the mean hours and minutes to FCB or test termination. We will calculate the time of complete protection for the test repellents. Therefore, the time to first confirmed bite for all treated test subjects will be averaged and the standard deviation computed. A 95% confidence limit will be determined. If a test subject protection time appears to be an "outlier" (one that appears to deviate markedly from the other members of the sample in which it occurs), that data will be subjected to the test for outlying observations as described in ASTM E 178-94 "Standard Practice for Dealing With Outlying Observations". If the test indicates that the observation is an outlier, that data point

If a test subject wishes to drop out of the study before the stated end point, the data from that test subject will not be used in calculating the mean PT of the test repellent. Any treated arms that do not breakdown within the twelve hour time frame of the study will be given a value of twelve for PT. All data will be entered into a CoStat program for the calculation of the standard deviation and the 95% confidence limit.

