With regard to the potential for irritation or allergic reactions to the test material, this risk has been greatly reduced by careful consideration of the components of the test material and avoidance of the use of known sensitizers and irritants. As an added precaution, subjects with a history of reaction to insect bites, insect repellents, and skin care products will be excluded from the study. Further, the subjects will be closely monitored during the study for signs of significant skin reactions and prompt medical attention will be obtained should an adverse reaction be experienced.

While the above risks are a concern to the study sponsor and the conducting laboratory, there are currently no viable alternatives to such human studies for determination of the performance characteristics of insect repellents. As indicated above, it is unlawful to distribute unregistered pesticide products, which include insect repellents. EPA requires that efficacy data collected from human studies be submitted for EPA review in order to obtain approval for an insect repellent registration. These data must substantiate the public health protection claims made on the product's labeling. Specifically, data are required to both substantiate the repellency of specific insect pests and provide the user realistic expectations of the protection time provided from each of those pests by the product.

While there is obviously an economic incentive to the sponsor of the study to offer a new insect repellent alternative to consumers, such products must offer a recognized benefit to consumers or they will simply not be purchased or used. It is important to bring new insect repellent products to market so that consumers have alternatives that they find personally acceptable and convenient to use to protect themselves and family members from irritating and potential disease-carrying insect bites. New products, such as the proposed test samples, have been formulated to provide protection from insect bites in combination with other benefits that promote consumer acceptance and use of the product (i.e., convenience of product form or method of application, fragrance preferences, preference for, or avoidance of, a specific active ingredient, etc.).

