#### BENEFITS

The purpose of this proposed insect repellent efficacy field study is to determine the protection time that can be reliably anticipated from use of these products. Field studies, such as the one proposed, have been long considered by the EPA (and the sponsor) to be the most realistic and reliable testing method available to predict protection time of a topically applied insect product. While the sponsor is an obvious beneficiary of the proposed test, the resulting information on the performance of the products will also directly benefit consumers because it will substantiate which insect pests will be repelled and provide realistic expectations for protection time. Clearly, both the study sponsor and consumers benefit from the performance of this study to provide the data required under FIFRA to substantiate this pesticide product's label claims. Specifically, FIFRA guidelines require human efficacy test data on insect repellents intended to be applied directly to the skin claiming to repel insect vectors such as mosquitoes.

Insect repellent products help prevent annoying bites and likely serve to decrease the potential spread of some diseases. It is known that consumers use insect repellents to help reduce the risk of WNV and other vector-borne diseases as stated by the CDC. The proposed study will attempt to substantiate that the test articles repel mosquitoes and will provide the user with a reliable estimate of protection time that can be anticipated under real-life conditions. It is important to bring such new products to market so that consumers can have access to alternative formulations that work best for them. That is, some formulations seem to provide longer protection times to certain individuals or simply be more convenient, pleasurable, or preferable to use (i.e., convenient product form or method of application, fragrance preferences, combination with sunscreen or skin care ingredients, aversion to or a preference for certain active ingredients, etc.).

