#### Number of subjects and Rationale for Sample Size

The EPA Guideline (EPA/OPPTS Guideline \$10.3700) recommends at least six test subjects be used. Because of the cost of doing field studies, it is prudent to ensure data collected will give a good representation of the repellency of the test formulations. In a published paper the number of subjects required to achieve an estimated among-subjects standard deviation for specific times of 0.5 hours to 2.0 hours was calculated for protection times from 1 hour to 8 hours. The number of subjects required to achieve an estimated among-subjects standard deviation of 2.0 hours at a 95% confidence level for an 8 hour protection time was calculated to be between 10 and 11 subjects. This study, therefore, will use ten treated test subjects. There will be an additional two control subjects, plus two additional treated test subjects to replace anyone that either drops out or is ineligible to participate due to a positive pregnancy test or other unforseen circumstances. These additional two treated test subjects will help to ensure a minimum "n" of ten and will aid in protecting the privacy of any dropouts.

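### The plan reports the mean time to first confirmed bite as the Protection Time and as complete protection, although the stated purpose is a time that can be reliably anticipated

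*Protocol*

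**What the plan says.** The Protocol uses one term in two senses. Under Study Rationale, Protection Time is an interval for one treated subject, from application to the first confirmed bite (FCB). Under Data Analysis it becomes a group average: "Efficacy data will be reported as Protection Time which is the mean hours and minutes to FCB or test termination". That section goes on: "We will calculate the time of complete protection for the test repellents". It then gives the method, which is to average the times over treated subjects and compute the standard deviation. It adds: "A 95% confidence limit will be determined". It does not say which parameter the limit is for, or whether it is one- or two-sided. Arms that have not broken down by 12 hours are scored as 12.

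The purpose is stated in terms of what a user can expect. Benefits says the study is to "determine the protection time that can be reliably anticipated from use of these products" and that it "will provide the user with a reliable estimate of protection time that can be anticipated under real-life conditions". Study Rationale says the required data must "provide the user realistic expectations of the protection time provided from each of those pests by the product". No median, percentile or proportion still protected is named among the reported results.

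**The concern.** A mean answers the question of how long protection lasts on average. A time that can be reliably anticipated also calls for some account of how early protection starts to fail. A confidence limit for a mean does not give that: it shows how precisely the average is known, and it closes in on the average as subjects are added.

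The label makes this worse. Under Test Site Location the Protocol speaks of complete repellency for products that repel all mosquitoes through the exposure period. By the mean time, a substantial share of arms will usually have had a confirmed bite, so describing the mean as complete protection invites misreading. Study Rationale says such data substantiate label claims, so a reader may well take the headline figure as time protected. The issue arises even if no arm reaches 12 hours, so it is separate from how those arms are scored.

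**Working it through.** **Inputs**
- Planning values, from Number of Subjects and Rationale for Sample Size: "an estimated among-subjects standard deviation of 2.0 hours at a 95% confidence level for an 8 hour protection time".
- Arms per product and site: 10 as the planned minimum (same section: "This study, therefore, will use ten treated test subjects") and 12 if everyone assigned to treatment is used (Experimental Design).
- Cap: 12 hours (Data Analysis).
- Assumptions: the limit is for the mean and two-sided; times are normal, with little capping at first.

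**The plan's own figure.** The section gives between 10 and 11 subjects. With n = (z × SD / d)², the half-width d is needed and is not stated, so the figure can be neither confirmed nor refuted:
- SD 2.0 h, one-sided 95%, assumed d = 1.0 h: (1.645 × 2.0 / 1.0)² = 10.8.
- SD 2.0 h, two-sided 95%, assumed d = 1.25 h: (1.960 × 2.0 / 1.25)² = 9.8.
- If 2.0 h is really the half-width: SD = 2.0 × √n / 1.960 = 3.2 h (n = 10) to 3.4 h (n = 11).

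**Share of users before the mean.** For symmetric times without capping this is 50%.

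**Share before the lower limit.** The limit is mean − t × SD/√n. The share of normal times below it is Φ(−t/√n), so mean and SD both cancel.

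| n | t (two-sided 95%) | t/√n | Lower limit at 8 h, SD 2.0 h | Share below |
|---|---|---|---|---|
| 10 | 2.262 | 0.715 | 8 − 1.43 = 6.57 h | 23.7% |
| 12 | 2.201 | 0.635 | 8 − 1.27 = 6.73 h | 26.3% |

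If the limit is one-sided the shares are 28.1% and 30.2%. With 24 arms, were the sites pooled, t/√n = 2.069/√24 = 0.422 and the share is 34%. More subjects raise the share.

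**Effect of the 12-hour cap.** Simulation with the sample SD and the cap, for normal and Weibull times, gave these average shares below the lower limit:
- True mean 8 h, SD 2.0 h: about 26% (n = 10) and 27% to 28% (n = 12). Single trials ranged from about 10% to 46% (5th to 95th percentile).
- True mean 12 h, SD 2 h: 21% to 23%.
- True mean 13 h, SD 2 h: 17% to 18%.

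Capping also lowers the share before the mean. For normal times with true mean 12 h and SD 2 h, the capped mean is 12 − 2 × 0.399 = 11.2 h, and Φ((11.2 − 12)/2) = Φ(−0.4) = 34%.

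**An early percentile, for scale.** The time by which 10% have a confirmed bite is mean − 1.2816 × SD:
- 8 h, SD 2.0 h: 5.4 h.
- 8 h, SD 3.2 to 3.4 h: 3.9 to 3.6 h.
- 12 h, SD 2 h: 9.4 h.

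Unlike the shares above, these hours depend heavily on the inputs.

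**What 10 to 12 arms can support.** A one-sided 95% normal tolerance bound covering 90% of users, at 8 h and SD 2.0 h, is 8 − 2.355 × 2.0 = 3.3 h (n = 10) or 8 − 2.210 × 2.0 = 3.6 h (n = 12), against a true 5.4 h. With SD 3.2 to 3.4 h the same factors give about 0 to 0.9 h. A distribution-free bound is not available: 0.9¹² = 0.28, well above 0.05.

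**The case against.** The best defence is that a mean with a 95% limit is a fair reading of a reliable estimate of expected performance. The purpose statements come from Rationale and Benefits prose; the Objective asks only for an evaluation of efficacy for up to 12 hours. The standard deviation will be computed and each arm's bite times recorded, so spread is not ignored. The section does not claim its limit is a tolerance limit. Extra summaries could also sit in a statistical analysis plan that is not shown here.

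Much of this stands, and it rules out three stronger readings:
- A reader might infer that the Protocol promises a time each user can rely on. It does not: it speaks of realistic expectations and a reliable estimate, and Benefits itself notes that protection differs between individuals.
- A reader might attribute the one-in-four share to the plan's 2.0 h standard deviation. The share follows from n and the t quantile under normality.
- A reader might conclude that a 90%/95% lower tolerance bound should be the headline. Nothing in the documents sets those levels, and 10 to 12 arms support such a bound poorly.

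What the defence does not remove is the label. Data Analysis itself fixes the headline statistic and its name, uses that name differently from Study Rationale, and presents an average as complete protection. A standard deviation from which a reader could work out a percentile is not a reported percentile.

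**Conclusion.** The concern holds as a mismatch between stated purpose and reported summary, together with a misleading label. It does not invalidate the mean or its limit as descriptions of average performance.

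Its size: about half of users would have a confirmed bite before the headline figure if times are roughly symmetric and few arms reach 12 hours, and about a quarter before the lower two-sided limit under normality. Both shares shrink as more arms reach 12 hours, which is what the sponsor hopes for, but they stay material. The figures rest on reading the limit as one for the mean, which is natural but not stated. Bitten here means a first confirmed bite; unconfirmed bites could come earlier. The doubtful meaning of the 2.0 h in the sample-size section does not affect the shares, only the illustrative hours.

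**What to change.** In Data Analysis:
1. Label the summary mean (average) PT, keep Protection Time for the individual interval defined in Study Rationale, and do not describe the mean as the time of complete protection.
2. For each product and site, report the proportion of arms still free of a confirmed bite at each half hour to 12 hours, with pointwise 95% limits.
3. From that curve, report the median and an early percentile, for example the time to which 90% of arms remain protected, and note that 10 to 12 arms estimate it imprecisely. Where the curve does not fall that far by 12 hours, say so.
4. State that the 95% limit is for the mean, and whether it is one- or two-sided.

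A parametric 90%/95% lower tolerance bound may be added with its assumptions stated, but not as the headline.

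The cost is wording and a short table from data already recorded; no further subjects or exposure are needed. The downside is that the early percentile will be shorter than the mean.
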